3. STUDY DESIGN

To address the primary and secondary hypotheses, this research study was designed as a randomized clinical trial comparing the manualized FORT-A treatment to treatment as usual for polytraumatic chronic musculoskeletal pain in the STVHCS Polytrauma Rehabilitation Center. Eligible OEF/OIF/OND Veterans will be randomized to either arm in 1:1 random permuted block randomization with no stratification. Because the FORT-A is a group intervention, it is vital that we randomize into meaningful blocks of at least three Veterans and no more than seven. Three is chosen as the lower block boundary because the PI had success in the original FORT trial with FORT groups of three active duty service members. Seven Veterans will be the upper boundary because FORT groups of more than seven military members were difficult to manage. In block randomization with static boundaries, study staff overseeing randomization will lose blinding if they are aware of how many participants have already been randomized into each block. For example, if block boundaries are always 5 participants and the treatment as usual condition has 5 participants while the active treatment has 4, then the staff randomizing the 10th participant will know with certainty that this participant will be in the active treatment group. To protect blinding, we have chosen to implement a variable boundary randomization for which the study staff randomizing patients will be blind to the boundaries and the resulting condition of the participant (see Sanghaei, 2011). The PI, Independent Evaluators, and Biostatistician will be blind to the condition of all participants until data lock. A research assistant overseeing randomization will also be blinded by randomizing unique patient identifiers into variable permuted blocks (through the STRONG STAR Data Core) by unique study identifier (e.g., first participant identified as #0001). All assessments given by Independent Evaluators will be labeled with just the unique identifier. Only the study coordinator (and co-coordinator) will be able to link unique identifiers to individual participants.

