sessions are audiotaped and 10-15% of all audiotaped group sessions will be selected for review by a trained independent evaluator who will use a structured checklist to ensure that all significant treatment elements are included in the intervention. Interns and Fellows will be formally trained in the manualized group intervention by [name] (who developed the intervention and created the manual) and will co-facilitate a group intervention with [name] at the PRC to practice the intervention in vivo. All groups will be documented in CPRS using a standard note template. The PI (and other blinded study personnel) will not review any of this documentation. CPRS notes for group and individual treatment components will be overseen and cosigned by [name] and [name].

Blinding: To maintain blinding, the PI will not be involved in any group interventions. Independent Evaluators (IEs) assessing group intervention facilitator adherence will be different people than the IEs responsible for assessments (because the assessing IEs may recognize voices on the tapes from their assessment experiences and may become unblinded as a result).

Providers and Qualifications: FORT-A Group Intervention will be delivered by STRONG STAR Clinical Psychology Interns and Postdoctoral Fellows (a total of 4 possible providers who will rotate through different groups). The structure of the manual and skills contained therein were developed for use by individuals with previous exposure to basic CBT and mindfulness skills commonly taught as part of the UTHSCSA Clinical Psychology Internship curriculum (and most other APA-Accredited Psychology Internships). Group intervention providers will be trained by [name] and will observe one iteration of the FORT-A Group with [name], [name], or [name] (all of whom have been trained on the components of the manual and who had a hand in developing the manualized intervention). To run the group without [name] or [name] present, the Intern or Fellow must be certified using the procedures outlined in Section 5.4 of this document.

Individual Psychotherapy

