A previous study completed by the PI in collaboration with [name] and [name] through the STRONG STAR PTSD Research Consortium revealed that a brief, Prolonged Exposure (PE) protocol can have a meaningful effect on PTSD symptoms, though PE in isolation did not appear to impact chronic pain symptoms. The PI has previously described how PTSD symptoms can interact and affect pain experience, so PTSD (and concomitant depression) must be addressed as part of this interdisciplinary intervention to ensure that PTSD does not act as a barrier to pain management intervention. Because of its success in the previous STRONG STAR trial, this study will use the brief PE manualized intervention used in the previous trial (5 sessions) with an additional session of behavioral activation (serving as the first session) to address depression symptoms. All STRONG STAR Interns and Fellows receive world class training in PE and their supervision will be overseen by [name], master trained in PE by [name] and [name], and [name] (also trained in PE through STRONG STAR). All individual sessions will be documented in CPRS.

Blinding: Neither [name] nor [name] are involved in assessment of participants and will be asked not to discuss specific (i.e., identifiable) details of the interventions with the PI or other study personnel blinded to treatment condition (see Figure 2).

Providers and Qualifications: Individual treatment providers must be certified in Prolonged Exposure for PTSD (PE) or supervised by a certified PE provider. Because of this, only STRONG STAR Interns and Postdoctoral Fellows or licensed Psychologists ([name], [name]) can provide individual intervention for this research (a total of 5 different providers). Individual providers must have completed a two-day training in PE (mandatory for STRONG STAR Faculty, Fellows and Interns) and must be certified in PE as described in Section 5.4 of this document. PE is commonly practiced and taught throughout the VA system, drastically improving the generalizability of this component of the treatment manual.

Biofeedback (Manual Under Development)

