6.2.2 Randomization and Baseline

Randomization (Wk -4 to 0)

Once the PI and Co-Investigators have determined that a participant has satisfactorily met all inclusion/exclusion criteria, the participant will be randomized by the study coordinator (this could be done at any time from week -4 to week 0 as long as consenting and screening come first). The date of randomization will be recorded on the Enrollment Log.

The maximum allowable time between enrollment and randomization is 4 weeks. If screening and determination of eligibility goes beyond this allowable window, the participant will need to be re-screened before randomization.

Baseline Assessments (Week 0; See Figure 4)

Baseline assessment occurs within 4 weeks from the time of enrollment (regardless of when baseline assessment occurs relative to screening, Baseline Assessment is identified as Week 0).

For participants who have successfully been screened for eligibility and are randomized into the study, baseline assessments are performed to measure the study outcomes. They also ensure that the groups are balanced with respect to baseline characteristics.

Baseline evaluations for this study include:

Assessments (Domain Assessed)	Assessment Window	Special Instructions
----------------------------------	----------------------	----------------------

Health Questionnaire / Addendum (previous pain treatments) (comorbid pain/medical conditions)	≤ 2 weeks before treatment start	Balance Sample Past medical history will not change, so this measure is only given once
Concomitant Medications and Medication Quantification Scale- III (medications that may impact pain) (medications that may impact mood)		Control: Other Medications Medications may change, so this will be assessed at all assessment visits; self-report and CPRS review
Timeline Follow-back Interview (opioid & other pain medication use)		Endpoint: Hypothesis 3 Assessed at all assessment visits
Oswestry Disability Index (self-report disability)		Endpoint: Hypothesis 1 Veterans cannot participate with moderate to severe TBI- related cognitive impairment
PHQ-9 (depression symptoms)		Endpoint: Hypothesis 2 Assessed at all assessment intervals
PTSD Checklist – 5 (PTSD symptoms)		Endpoint: Hypothesis 2 Assessed at all assessment intervals

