Study Design and Rationale: To test the primary hypothesis, the proposed research needs to simply determine that the experimental intervention (FORT-A) is superior to treatment as usual. The unique requirements of the VA and DoD systems preclude a truly controlled trial (i.e., military and VA IRBs will not approve research denying access to treatment for their covered constituents). Thus, FORT-A cannot be compared to a no-treatment control condition. Because of the variability in chronic pain intervention in the VA system, definition of treatment-as-usual can be difficult. In the original FORT trial, we chose to compare the FORT program to the best available intervention that the DoD had to offer for chronic pain. If FORT was truly an innovative and high-impact intervention, then it should be better than anything else that the military was using to manage chronic pain. Similar logic applies to the present study. FORT-A was developed to improve upon the original FORT program for application to a more complex patient population than that treated in the FORT study. Fortunately, the best available intervention for complex chronic pain in the VA right is through the Polytrauma Rehabilitation Center, making the PRC a natural comparator for this study. Better yet, the PRC is a structured, interdisciplinary program in which all enrolled participants have access to PT services and an interdisciplinary treatment team. If FORT-A is a truly innovative and high-impact intervention, then it should out-perform the PRC (which has openly expressed difficulty in managing chronic pain; Strasser et al., 2008; Clark et al., 2009; Friedemann-Sanchez et al., 2008). Thus, the most parsimonious design for this research is a two-arm, randomized clinical trial comparing 3 weeks of FORT-A to 3 weeks of PRC intervention. After completion of the three week intervention phase, all participants will be permitted to seek additional treatment through the VA system (which is mandated by the VA IRB). We will track treatment engagement through a review of the VA electronic medical record (CPRS, to which all study team members will have access) and interviews with participants at all follow-up assessment intervals.

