Study personnel blind to participant randomization can use the VA electronic health record (CPRS) to identify active and new opioid medication prescriptions from providers working in the VA system. Study physicians ([name] and [name]) get free access to the Prescription Access in Texas (PAT) prescription monitoring program to examine any and all Schedule II through V medications given by any provider in the State of Texas. Both CPRS and PAT (which maintains records of medications dispensed to a patient for 365 days) will be accessed at each Veteran's one-year follow-up visit to identify medications prescribed over the one-year study participation period.

Psychosocial Trauma and Emotional Measures will be adjudicated through the STRONG STAR Assessment Core using existing SOP for surveillance and adjudication of these measure. STRONG STAR has implemented this process for military and VA studies serving thousands of study participants across dozens of

studies (see Appendix J).

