10. DATA COLLECTION AND QUALITY ASSURANCE

10.1 Data Collection Forms

Data will be collected by an Independent Evaluator blind to the randomized condition of the participant and entered into an online SQL database on the STRONG STAR server that is designed specifically for this study. As described in the STRONG STAR Data Entry SOP (see **Appendix S**), data are double-entered to minimize transcription errors and all data entry forms include appropriate data entry masks that limit the format and scope of entered data (to ensure that out-of-range values are not erroneously recorded) with provided feedback if entered data exceed expected ranges. STRONG STAR has developed strict rules guiding the translation of assessment measures and data recording forms into digital formats as outlined in **Appendix T**. Paper copies of assessments are also uploaded and tagged to the assessment record for review by the IEs or other study staff if adjudication of responses is needed. The STRONG STAR Network is FISMA compliant and has received permission from the VHA for the storage of Veteran study data (which is very strictly controlled by the VA system). Because the STRONG STAR Database is accessible through a secure internet portal, data can be entered into the system directly from any VA computer with internet access (of which this study currently has dedicated access to two through the PRC). To ensure confidentiality of patient records, all data are entered into study records using the participant's unique ID. A link between identifiers and the ID is maintained in a separate data table with access restricted to individuals who are not blind to patient identifiers (e.g., study Coordinator, interventionists).

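### The evaluator blind is left unprotected: the plan does not say who reviews CPRS or asks about treatment received, and CPRS holds FORT-A session notes

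*Combined protocol and SAP*

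**What the plan says.** **Who is blind.** Section 3: "The PI, Independent Evaluators, and Biostatistician will be blind to the condition of all participants until data lock". Section 6.2.3 repeats that IEs do not know the condition of those they assess. Section 10.1: "Data will be collected by an Independent Evaluator blind to the randomized condition of the participant". Sections 9.5.1 and 9.5.2 have a blinded IE give the ODI and the TLFB.

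**What is in the record.** Section 5.2 on FORT-A groups: "All groups will be documented in CPRS using a standard note template". On individual psychotherapy: "All individual sessions will be documented in CPRS". It also has notes for all FORT-A physical therapy encounters entered in CPRS. Biofeedback is to have clinical documentation, but CPRS is not named. Section 7.2 has physical therapy and psychotherapy notes entered within 24 hours.

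**Who goes into the record, and who asks about treatment.** The section 6.2.2 entry for concomitant medications and the MQS reads: "Medications may change, so this will be assessed at all assessment visits; self-report and CPRS review". Section 9.5.2: "Study personnel blind to participant randomization can use the VA electronic health record (CPRS) to identify active and new opioid medication prescriptions". Section 9.1: "We will track treatment engagement through a review of the VA electronic medical record (CPRS, to which all study team members will have access", and it adds "interviews with participants at all follow-up assessment intervals".

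**The safeguard.** Directly after the sentence on group notes, section 5.2 says that the PI and other blinded personnel will not review that documentation.

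**The concern.** The TLFB is a semi-structured interview in which the evaluator helps the participant reconstruct 30 days of pill use. Recidivism is opioid use on three or more days in 30, so one recalled day, two against three, changes a participant's status. An interviewer who knows the arm can probe harder in one arm than in the other, without intending to. Section 9.2 accepts that participants cannot be masked, so the evaluator blind is the main protection the plan offers for this endpoint.

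The plan recognises much smaller threats. Section 5.2 separates fidelity raters from outcome evaluators because an evaluator might recognise a voice on a recording. Reading a chart that contains FORT-A notes, or asking what treatment someone has had, is a more direct exposure. Section 6.2.3.1, on maintaining the blind, deals with recordings, fidelity raters, data entry and case numbers in meetings. It does not deal with CPRS access or with participants describing their treatment.

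**Working it through.** No figure in the plan is in dispute and no power or error-rate formula applies. The check sets the sections side by side.

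1. **Is the IE required to be blind?** Yes: sections 3, 6.2.3, 9.5.1, 9.5.2 and 10.1 agree.

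2. **Does CPRS reveal the arm?** Planned FORT-A sessions explicitly placed in CPRS are 12 group + 12 physical therapy + 6 individual = 30. Adding 6 biofeedback sessions would give 36, but their place in CPRS is not stated. The group notes are the clearest marker of the arm. Physical therapy and individual notes are weaker markers: usual-care participants may attend physical therapy (5.1.1), and some individual sessions may be pre-existing care from another provider (5.1).

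3. **Are blinded staff kept from those notes?** The statement that they will not review them follows the group-note sentence only. The remaining 30 − 12 = 18 sessions have no matching statement. For these, section 5.2 restricts only what interventionists and supervisors tell blinded staff. Nowhere is there a medication-only view, an access restriction, or a rule that outcomes are rated before the chart is opened.

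4. **Do blinded staff enter CPRS?** Section 9.5.2 permits it for opioid prescriptions. Section 6.2.2 requires a CPRS medication review but names no role. Section 10.1 has the IE collect the data, and section 9.5.2 has the IE discuss each participant's TLFB and MQS data with the Coordinator within two business days. That makes the IE the natural reader of the chart, but this is an inference.

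5. **When?** The sections differ. Section 6.2.2 says every assessment visit. Section 6.2.5 names CPRS, together with the Texas prescription database (PAT), only at Visit 16, and section 9.5.2 places that look-up at the one-year visit. Section 6.2.4 does not mention CPRS at Visits 14 and 15.
   - If the chart is reviewed at every visit, exposure can begin at post-treatment. It would then precede the 6- and 12-month visits and any of the 11 monthly phone TLFBs done by the same person.
   - If it is opened only at one year, the chart route threatens at most the one-year TLFB, and only if the chart is read first.

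6. **The interview route.** Section 9.1 has participants interviewed about treatment at all follow-up intervals, under either reading of step 5. A participant who describes three weeks of group pain classes and group exercise has disclosed the arm. The interviewer is not named, and nothing keeps this interview apart from, or after, the TLFB.

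**The case against.** The strongest reply is that this is silence about roles, not a failure of blinding. Section 6.2.2 and section 9.1 assign nobody. Section 9.5.2 says blinded staff can use CPRS, and only to look for prescriptions; access is not a duty. Non-IEs collect other data: physical therapy staff and students record functional capacity, study physicians consult PAT, and interventionists keep the attendance logs. Section 5.2 bars blinded staff from the most revealing notes, and its next sentence mentions group and individual notes together, so a generous reader might extend the bar to both. Figure 2, which sets blinding by role, and the SOP appendices were not available to this review and may settle the matter.

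Much of this stands. A reader might infer that IEs must read the chart, that every FORT-A session is in it, that each of three post-baseline visits includes a chart review, and so that the blind is broken before the later outcomes. The documents do not support that. No role is named, biofeedback is not placed in CPRS, two sections tie the CPRS look-up to one year, and a stated intention not to read the group notes exists.

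The reply does not remove the gap. Even the generous reading leaves physical therapy notes uncovered and gives no means of searching the record without meeting session notes. The interview route does not depend on CPRS at all. Whatever Figure 2 assigns, sections 5.2, 6.2.2, 6.2.5, 9.1 and 9.5.2 still need to agree.

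**Conclusion.** The concern holds as an unprotected route to unblinding, not as a demonstrated breach. Followed as written, sections 6.2.2 and 9.5.2 can send blinded personnel into the record that holds up to 30 FORT-A sessions per participant. Section 9.1 also sets up a conversation about treatment at every follow-up with nobody assigned to hold it.

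The direction and size of any bias cannot be computed from the documents. The exposure falls mainly on the interviewer-administered TLFB. The ODI is self-reported by participants who know their arm, so the evaluator blind protects it little in any case, and the same applies to the other self-completed questionnaires. It would be wrong to infer that the primary outcome is compromised to the same degree.

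The conclusion assumes that the IE, as data collector, is at least a candidate for the chart review and the treatment interview, and that no unseen figure or SOP assigns both elsewhere. It merits correction because the remedy is inexpensive.

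**What to change.** Amend sections 5.2, 6.2.2, 9.1 and 9.5.2 as follows.

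1. State that IEs who assess outcomes do not open a randomised participant's CPRS record. Qualify the team-wide access statement in 9.1 and the permission for blinded personnel in 9.5.2 to match.
2. Assign the CPRS and PAT medication review to an existing non-rater, for example the study physicians who already have PAT access, or the Coordinator. Only medication data should pass to the assessment file.
3. Have a non-rater collect treatment received, after the IE has completed and entered the TLFB and ODI for that visit.
4. Reconcile the timing of the CPRS review: all visits in 6.2.2 against the one-year visit in 6.2.5 and 9.5.2.
5. Reconcile the Coordinator's status. The randomization text in 6.2.2 says the Coordinator is blinded to all assignments, whereas 6.2.3 and 9.2 say the Coordinator knows them. If the Coordinator takes on either task, 6.2.3 must also change, because it keeps the Coordinator out of assessment and blind to outcomes.

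The cost is protocol wording, modest time from existing staff, and medication data that reach the file slightly later. Having IEs record a guess of the arm, or sealing the treatment helpfulness questionnaire from them, is optional and not needed for the fix.

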6.2.3 Blinding

Blinding in an interdisciplinary behavioral intervention is extraordinarily difficult since the intervention requires face-to-face contact and continuity of an interdisciplinary approach requires different interventionists to be able to talk to one another about patient progress. This is particularly true in trials of openly symptomatic conditions (like chronic pain; see Friedberg, Lipsitz, & Natarajan, 2010). There is no placebo control for an intervention like this (nor would the VHA allow one), so blinding is best accomplished through careful consideration of “need to know” privileging. Figure 2 provides a visual representation of who needs blinding and who is allowed to maintain awareness of patient identity. The entire study staff will be thoroughly briefed on the importance of maintaining blinding and the study coordinator will attend all study meetings and help ensure that blinding is maintained when blinded and unblinded personnel discuss the study participants. We have chosen to use a multi-level blinding scheme (as described by Friedberg et al.) in which study personnel will be blinded to randomized treatment **condition**, assessment **outcomes**, or **both** (as shown in Figure 2).

Study interventionists and their supervisors (for group psychosocial treatment; individual psychotherapy; biofeedback, and physical therapy) cannot be blinded to **condition** because they will be aware of the treatment condition of the patients they treat. Research Assistants (RA’s), blinded to participant identity, will listen to audio recordings of treatment sessions and will rate adherence to the treatment manual using a standardized checklist (see Section 10.3 Quality Assurance) for more information about this. The Research Coordinator and Co-Coordinator will be aware of participant condition (because they are responsible for randomizing and because they need to assist with adverse events monitoring and administrative oversight of treatment and assessment procedures), but they will be blinded to **outcomes**. The Coordinator and Co-Coordinator will not be directly involved in treatment or assessment and will be asked to only refer to participants by their unique identifiers when discussing participants with RA’s, the PI, or IE’s. Independent Evaluators will

become aware of outcomes during the course of their assessments, but will be blind to **condition** of the participants they assess.

